The proposed study aims to conduct a randomized controlled trial in order to implement culturally adapted cognitive behavioral intervention (CA-CBI) to COVID-19 survivors and evaluate the effectiveness of the intervention in reducing psychological distress for this particular group. Individuals who are 18 years or older, who got infected with COVID-19 and currently recovered, and who have a considerable amount of psychological distress will be included to the study. Individuals who have a severe mental disorder or suicidal risk will be excluded from the study. For screening purposes, an online survey followed by a structured interview will be conducted to identify the eligible participants. In the intervention part, CA-CBI will be implemented in a group format on Zoom which is an online platform with HIPAA compliance. For this purpose, the CA-CBI manual will be revised to the sample of COVID-19 survivors and the problems they are experiencing during the COVID-19 pandemic. Participants in the control group will receive online leaflets including a brief psychoeducation and appropriate referrals to receive free psychosocial support. To test the effectiveness of CA-CBI, all participants will be assessed one week before the intervention (pre-test), one week after the intervention (post-test), and one month after the post-test (follow-up). During the assessment, participants will be asked about psychological distress, symptoms of depression, anxiety, post-traumatic stress and somatization, as well as, questions about their quality of life, psychological flexibility and emotion regulation. The primary outcome is the psychological distress at the follow-up phase. A process evaluation will be conducted in order to assess the treatment fidelity and possible facilitators and barriers during the implementation of online-delivered group CA-CBI.

This project consists of 3 stages:

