In the first stage, participants will be reached through social media and online communication channels and will be asked to fill out an online survey for screening purposes. Participants agreeing on the informed consent will be able to answer questions about demographics, COVID-19 related data (infection, recovery, etc.), psychological problems and suicidal risk. Participants who were infected with and recovered from COVID-19 will be able to continue with the Kessler-10 Psychological Distress Scale (K10). Those who score higher than 15 will continue to the suicidality questions. In this part, participants who are detected to have a suicidal risk will see a referral list on the screen where they can receive free psychological help for their suicidal ideations. Also, they will receive the phone number of the research team on the screen in case if they need to obtain more information about the referrals and to reach the research team. Participants who got infected with COVID-19 and recovered, who score a considerable amount of psychological distress ( $K > 15$ ), and who do not have a suicidal risk will be invited to the next stage of the screening procedure. In this

stage, the Structured Clinical Interview for DSM-5 (SCID-5) will be conducted with participants to screen any severe mental disorders. The structured interview will be conducted via Zoom and participants who have no severe psychiatric condition will be asked whether they would like to attend an intervention to decrease their psychological distress. After conducting SCID-5, eligible participants who agree to participate to the intervention will be included to the study and will be given the pre-test assessment one week before the intervention. Pre-test survey will take approximately 20 minutes. It is aimed that 86 participants who meet the inclusion criteria would participate to this phase of the study. The links of the surveys which will be created on Qualtrics will be shared on social media and online communication platforms. On these links, participants will first see the information about the study, and after giving consent to participate in the study, they will be able to complete the questionnaires.

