In the second stage, eligible participants who agree to participate to the study will be randomly assigned to intervention (CA-CBI) group or control [enhanced treatment as usual (ETAU)] group. The required sample is identified as 86 participants for this stage. During the intervention, participants in the intervention group will receive online group CA-CBI for 8 weeks. Participants in the control group will receive a brief psychoeducation about their psychological distress as well as a referral list to consult appropriate places due to their psychological distress. In order to test the effectiveness of the CA-CBI for COVID-19 survivors, post-test assessment will be conducted with participants in the intervention and control group one week after the intervention. Participants in the control group will additionally be asked whether they received any psychological support during this process. To be able to observe the long-term effects of the CA-CBI, follow-up assessment will be conducted one month after the post-test. After all measures are completed, participants in the control group will be able to receive the intervention.

In the third stage, a process evaluation will be conducted to assess the treatment fidelity and the feasibility of implementation of the CA-CBI to COVID-19 survivors in an online group format. Interviews will be conducted with 5 completers, 5 drop-outs and 2 facilitators in order to evaluate the possible facilitators and barriers of attending/delivering the online group sessions.

The data will be analyzed by using a statistical package called IBM SPSS 26.0. The effectiveness of the intervention will be tested by comparing the changes in the scores of primary outcome measure (K10) and secondary outcome measures (PHQ-9, GAD-7, PCL-5, SCL-90-R Somatization subscale, WHOQOL BREF) between the baseline and follow-up measure. Mediation analyses will be conducted to explore the mechanisms of change by using the Psychological Flexibility Scale and Emotion Regulation Questionnaire.

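### The primary K10 analysis names no model, covariate or arm contrast; specify follow-up K10, CA-CBI versus ETAU, adjusted for pre-test K10

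*Combined protocol and SAP*

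**What the plan says.** The overview in The Study Protocol fixes the outcome and time point: "The primary outcome is the psychological distress at the follow-up phase". It also sets the schedule: "all participants will be assessed one week before the intervention (pre-test), one week after the intervention (post-test), and one month after the post-test (follow-up").

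The second-stage paragraph states that participants "will be randomly assigned to intervention (CA-CBI) group or control [enhanced treatment as usual (ETAU)] group" and gives the size: "The required sample is identified as 86 participants for this stage". It does not state the allocation ratio.

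The closing data analysis paragraph has the only sentence on how the primary outcome is tested. Effectiveness is to be assessed by "comparing the changes in the scores of primary outcome measure (K10") and the secondary measures "between the baseline and follow-up measure". SPSS 26.0 is named; a test, model or covariate is not.

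K10 is also scored at the online screen, where it acts as an entry filter: "Those who score higher than 15 will continue to the suicidality questions".

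**The concern.** The overview and the analysis paragraph agree that the target is K10 at follow-up, assessed through change from baseline. What is missing is the analysis. Taken alone, the sentence does not say that the changes are compared between arms. Read in the light of the design, as it should be, it still admits two analyses: the difference between arms in mean change, or a comparison adjusted for pre-test K10.

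Two things are at stake.

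- **Precision.** A change score subtracts the whole pre-test value, whatever its correlation with follow-up. Unless that happens to be the right amount, chance imbalance at pre-test is over- or under-corrected. In a trial of 86 this can cost appreciable power.
- **An open choice.** Since neither analysis is fixed, the choice can be made after the results are known. The two can disagree on significance, and picking the favourable one raises the false-positive rate.

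A smaller point: baseline most naturally means the pre-test, but K10 is also taken at screening, so the text should say which.

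**Working it through.** **Inputs from the documents.** Total sample 86; two randomised arms; K10 at pre-test and follow-up in all participants; screening K10 above 15.

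**Assumptions (not in the documents).** 43 per arm; two-sided 5%; true difference 0.5 follow-up SD; no dropout or clustering; a common slope of follow-up on pre-test. The correlation r and the ratio k = pre-test SD / follow-up SD are ranged.

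**The plan's own figure.** The 86 cannot be reproduced, because no significance level, power, effect size, SD or dropout is given. For orientation, a simple comparison of two means with 43 per arm detects (1.960 + 0.842) × sqrt(2/43) = 0.60 SD at 80% power, or 0.70 SD at 90%.

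**Step 1: variances.** Per person, with follow-up SD set to 1:

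- change score: 1 + k² − 2rk
- adjusted for pre-test: 1 − r²
- difference: (k − r)², never negative and zero only when r = k

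At k=1, r=0.5 these are 1.00, 0.75 and 0.25. With equal SDs the ratio adjusted/change is (1+r)/2, that is 0.65, 0.75 and 0.85 at r=0.3, 0.5 and 0.7; simulation with 6,000 trials per setting gave 0.655, 0.752 and 0.855. Estimating the slope multiplies the adjusted variance by about 1 + 1/82, which is 1.2% in variance or 0.6% in SE. This cost is included in the power figures below.

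**Step 2: power.** Noncentral t, df 84 (change) and 83 (adjusted). Cells show change score / adjusted, in %.

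| k | r=0.3 | r=0.5 | r=0.7 | r=0.9 |
|---|---|---|---|---|
| 0.8 | 57 / 67 | 71 / 75 | 89 / 89 | >99 / >99 |
| 1.0 | 49 / 67 | 63 / 75 | 84 / 89 | >99 / >99 |
| 1.2 | 42 / 67 | 54 / 75 | 75 / 89 | 99 / >99 |

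**Step 3: the same loss as sample size.** The total a change score needs to match the adjusted analysis at 86 is 86 × (1 + k² − 2rk)/(1 − r²), ignoring degrees of freedom. At k=1, r=0.3 this is 86 × 1.40/0.91 = 132.

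| k | r=0.3 | r=0.5 | r=0.7 | r=0.9 |
|---|---|---|---|---|
| 0.8 | 110 | 96 | 88 | 91 |
| 1.0 | 132 | 115 | 101 | 91 |
| 1.2 | 163 | 142 | 128 | 127 |

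**Step 4: the source of the loss.** The arm difference at pre-test has SD sqrt(2/43) = 0.216 pre-test SD, so it exceeds 0.2 SD in either direction in about 35% of trials. With k=1, a 0.2 SD imbalance moves the change-score estimate by (1 − r) × 0.2 = 0.14, 0.10, 0.06 or 0.02 SD at r = 0.3, 0.5, 0.7 or 0.9. The adjusted estimate is not moved.

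**Step 5: the open choice.** Simulation, 40,000 bivariate-normal trials per cell, r = 0.3/0.5/0.7/0.9.

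- True difference 0.5 SD: both analyses average 0.50 in size in every cell, so there is no bias. One is significant and the other not in 24/18/8/0% of trials (k=1), 17/9/2/0% (k=0.8) and 32/27/17/1% (k=1.2).
- No true difference: each test alone rejects in 4.7-5.2% of trials. Taking whichever is significant gives 6.2-7.6% (k=1), 5.7-7.0% (k=0.8) and 7.8-8.3% (k=1.2).

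**Step 6: compatibility with the protocol wording.** With pre-test K10 as a covariate, modelling follow-up K10 or the change in K10 gives the same arm estimate and SE. In one simulated data set both gave −0.4430, SE 0.1988.

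**The case against.** - **The contrast is clear from the design.** The protocol describes a randomised controlled trial and takes post-test measures in both arms to test effectiveness. This stands: a before-after reading is possible only out of context. It does not supply a model or a covariate.
- **The gain may be small.** The only argument in the documents about k is that the entry rule may narrow the pre-test spread and put k below 1. There the gain shrinks: at r=0.3/0.5/0.7 it is 10/4/0 points for k=0.8, about 7/2/0 for k=0.7 and 4/0/0 for k=0.6. The documents give no reason to expect k=1.2, so its larger figures are an upper case. Restricting pre-test scores also tends to lower r along with k, so not every cell is equally plausible; k=0.8 with r=0.9 implies a slope above 1. This stands as a limit on size.
- **Adjustment is not always at least as precise.** At k=r=0.7 power is 89.4% for the change score and 89.1% adjusted, because the slope must be estimated. With 2:1 allocation and strongly different slopes in the two arms, one constructed case gave an adjusted variance 8% larger. With 1:1 allocation and different slopes, adjustment still won (variance ratio 0.77). The first loss is trivial, and nothing in the documents suggests the second setting.
- **Absolute power will differ in the real trial.** Delivery is in groups and drop-outs are expected. The tables are therefore a comparison of two analyses, not a forecast.
- **No selective choice is suggested.** True, and the inflation is modest. Naming the model in advance removes the question.

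**Conclusion.** The concern holds. The sole primary-analysis sentence leaves the model and covariate open and does not state the arm contrast, which must be inferred from the design. No bias follows, because both candidate analyses estimate the same effect.

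Apart from a small-sample cost of about 0.6% in SE, the adjusted analysis is never less precise under 1:1 allocation and a common slope. The gain runs from nothing, when r is close to k or very high, to about 17 points of power at k=1, r=0.3; it would be larger only if the pre-test spread exceeded that at follow-up. The power figures rest on assumed values of r, k, effect size and allocation; the variance inequality does not depend on r, k or the effect size. The case for fixing one analysis in advance does not depend on any of these values.

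This should be fixed, but it does not threaten the validity of the design.

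**What to change.** Add to the data analysis paragraph:

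*The primary analysis is the difference between CA-CBI and ETAU in mean K10 at follow-up (one month after the post-test), with 95% confidence interval, from a linear model with arm and pre-test K10 as terms. Pre-test K10 is the assessment made one week before the intervention, not the screening K10.*

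Use the same form for PHQ-9, GAD-7, PCL-5, SCL-90-R Somatization and WHOQOL-BREF, each with its own pre-test value. Label any unadjusted or change-score result as supportive. State the allocation ratio, since the precision argument is cleanest at 1:1.

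The cost is wording only. Pre-test values are already planned for everyone, the model is standard in SPSS, and no participants, visits or measurements are added. The change fixes outcome, contrast and covariate; missing follow-up data and clustering by therapy group are separate matters that it does not settle.

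### Must the plan fix the visits, outcome and model for its exploratory mediation analysis?

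*Combined protocol and SAP*

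**What the plan says.** All of the relevant text is under the heading The Study Protocol.

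- **Mediation.** The last sentence of the data analysis paragraph is the only text on it: "Mediation analyses will be conducted to explore the mechanisms of change by using the Psychological Flexibility Scale and Emotion Regulation Questionnaire".
- **Schedule.** The overview paragraph sets three assessments: "one week before the intervention (pre-test), one week after the intervention (post-test), and one month after the post-test (follow-up").
- **Content of the assessments.** The same paragraph lists "questions about their quality of life, psychological flexibility and emotion regulation" without limiting them to particular visits.
- **Primary outcome.** "The primary outcome is the psychological distress at the follow-up phase".
- **Effectiveness comparison.** The sentence before the mediation sentence compares changes "between the baseline and follow-up measure". It covers K10 and the "secondary outcome measures (PHQ-9, GAD-7, PCL-5, SCL-90-R Somatization subscale, WHOQOL BREF"). It does not mention the two mediator scales.
- **Software.** "The data will be analyzed by using a statistical package called IBM SPSS 26.0". This is a package, not a model.

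**The concern.** A mediation claim needs an order of events: treatment changes the mediator, and the mediator then changes the outcome. The sentence leaves that order open. If mediator and outcome both come from the follow-up assessment, the data cannot distinguish better flexibility lowering distress from lower distress raising flexibility scores. Carrying the neighbouring baseline-to-follow-up contrast over to the mediators would produce exactly that concurrent pairing.

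Two things would be at stake. A same-visit association could be reported as a mechanism. And with outcome, visits and adjustment unspecified, a reader could not tell whether the reported model was chosen before or after the results were seen.

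**Working it through.** **1. No planned figure to reproduce.** The only statistical figure in the documents is the total of 86 participants. It comes without alpha, power or effect size and is not tied to mediation.

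**2. Count the pairings.** A pre-test mediator precedes the intervention, so it can be a covariate but cannot carry the effect. That leaves post-test and follow-up. If the mediator may not be measured after the outcome, the pairs (mediator/outcome) are post-test/post-test, post-test/follow-up and follow-up/follow-up: 3 in all, 1 of them ordered. For follow-up K10 there are 2, of which 1 is ordered.

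**3. Count the analyses that fit the text.** There are 2 mediators and 6 outcomes (K10 plus 5 secondary measures).
- Follow-up outcomes: 2 × 6 × 2 = 24.
- Adding the post-test/post-test pairing: 2 × 6 × 3 = 36.
- Follow-up K10 alone: 2 × 2 = 4.

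**4. What the schedule can show.** The second-stage paragraph says "participants in the intervention group will receive online group CA-CBI for 8 weeks". Pre-test to post-test is therefore about 1 + 8 + 1 = 10 weeks with no assessment in between. The order of change during treatment is unobserved under any model, and analysis wording cannot alter that.

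**5. Is there one model the plan should have named?** A simulation tests this. Only N=86 comes from the documents. Everything else is assumed:
- 43 per arm, no drop-out, no group clustering
- effect on the driving variable 0.5 or 0.8 SD
- loading of the other variable on the driver, at the same visit, 0.4 or 0.6
- visit-to-visit autocorrelation of the driver 0.5 or 0.7
- K10 reliability 1.0 or 0.85

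This gives 2 × 2 × 2 × 2 = 16 scenarios per causal direction. Every model adjusts for pre-test mediator and pre-test K10. The first figure is the range over the 16 scenarios (2000 trials each). The figure in brackets is the range from separate simulations (400 to 800 trials per scenario) that also vary how strongly the non-driving variable persists between visits.

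| Model for follow-up K10 | Estimated mediated share, truth 0% (distress drives mediator) | Estimated mediated share, truth 100% (mediator drives distress) |
|---|---|---|
| Follow-up mediator | 16–42% (12–53%) | 95–102% (80–109%) |
| Post-test mediator | 8–20% (6–20%) | 48–72% (44–84%) |
| Post-test mediator, also adjusting for post-test K10 | 0–6% (0–6%) | 16–43% (−3 to 76%) |

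When the truth is 0%, both paths reach p<0.05 in 16–72%, 6–61% and 1–9% of trials for the three models in turn (12–88%, 4–62% and 1–9% with persistence varied).

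The same-visit model errs most when there is no mediation and least when mediation is complete. The time-ordered models do the reverse. The bottom-right cell depends almost wholly on the persistence assumption: with persistence varied, the chance of detecting a fully true mediator runs from 3% to 81%, so no particular power can be attached to that model. The scenarios are also two extremes with same-visit effects. None has a delayed effect of the post-test mediator on follow-up distress, which is the case the ordered pairing is meant to detect. The percentages are illustrations and do not rank the models.

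**The case for a change.** The strongest case for a change is that it is cheap and the choice matters. Two or three sentences would name post-test mediators, follow-up K10 and adjustment for the pre-test values, with no new data. The aim is to learn about mechanism, a same-visit model cannot show order, and an exploratory label does not tell a reader which of 24 analyses was planned. The simulations bear out that visit and adjustment move the estimated share materially.

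Much of this stands. The detail is absent, the 1-of-2 count is right, and settling outcome, visits and baseline covariates before analysis is good practice. What does not stand is the step from there to a defect. The plan does not prescribe the same-visit analysis; applying the baseline-to-follow-up contrast to the mediators is a reading the text does not make. The natural candidate for a fixed model recovers only 48–72% of a complete effect in the main simulation and still has both paths significant in up to 61% of trials where there is none, so naming it would be a preference rather than a correction. The whole analysis paragraph is equally brief: the effectiveness sentence states no model, covariates or alpha either, and the exploratory sentence is the least consequential place for that brevity.

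**Conclusion.** No change to the plan is needed. This is a gap that a competent analyst fills sensibly. The aim is exploratory, no decision is tied to the result, the primary K10 comparison is untouched, and the three assessments already supply a pairing with the mediator one month before the outcome.

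Its size is 2 open pairings for follow-up K10, 1 of them ordered, and 24 single-mediator analyses across follow-up outcomes. That count assumes both mediator scales are given at every assessment, as the overview implies. The simulated shares rest on assumed inputs apart from N=86 and support only one statement: in the cases examined, no single model is right in both causal directions.

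Ordinary practice covers the rest: settle outcome, visits and baseline covariates before analysis, and report that the mediators were not randomised and that evidence on order is limited.
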